Study design: This randomized controlled trial will compare outcomes on delirium, falls, sitter utilization (1:1's) and restraints between the two study groups: HELP-protocolized avatars, and usual care. Each day of the study, enrollment of subjects will proceed with randomization of each subject between groups (the randomization primarily effects delirium data, which is assessed by subject) until there are no more available intervention devices. However, falls and other unit-level grouping are non-randomized (see below).

Sample Size: A total of 3,650 patients (avatar and usual care) are expected to be enrolled at JHMC over the course of two years, based on an estimated average length of stay of 4 days.

Study Units: Patients will be recruited from the following units at JHMC: 3S, 3N, 4S, IMCU, 5N, 6S, and Hospice. Because the hospital only collects/reports unit-by-unit quarterly falls data, we will take the following measures to ensure that falls data collected for study purposes are a valid indicator of possible intervention effect:

- There are expected to be protocol and technical adaptations made during the first quarter of the study, and the study will not begin enrolling subjects exactly at the start of a calendar quarter. Therefore, the first calendar quarter of falls data is not intended to provide useful data regarding unit-level falls outcomes, and enrollment of patients may be performed on select units by convenience.
- Starting on the first day of the first full calendar quarter, a unit-equitable enrollment protocol will be implemented in which one or more of the study units at any time may be formally designated for active subject enrollment, and such designated study units will have their enrollment numbers monitored and rounding adjusted as needed to ensure that, on average, each designated unit receives a similar number of intervention patients at any time. Which units are designated or not designated for enrollment may be changed at the start of each calendar quarter to compare the effect of the intervention and to control for annual changes in fall rates. Research assistants will not enroll any patients on units not designated for enrollment, but will continue to round currently enrolled patients until they are dis-enrolled.

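### Unit-level falls comparison relies only on optional switching of units and uses no pre-study quarters, so depending on the schedule the effect may be inseparable from the units' own fall rates or imprecise

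*Combined protocol and SAP*

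**What the plan says.** Specific aims/hypotheses lists falls, and falls with injury, as the second aim. Study design states that "falls and other unit-level grouping are non-randomized". Study Units gives the reason, which is that "the hospital only collects/reports unit-by-unit quarterly falls data", and names seven units: "3S, 3N, 4S, IMCU, 5N, 6S, and Hospice".

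Study Units then lists measures meant to make these data a valid indicator of effect:
- The opening partial quarter is set aside: "the first calendar quarter of falls data is not intended to provide useful data regarding unit-level falls outcomes".
- Among designated units, numbers of intervention patients are kept similar.
- At any time "one or more of the study units at any time may be formally designated for active subject enrollment", and the designation may be changed at each quarter start "to compare the effect of the intervention and to control for annual changes in fall rates".

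Only the last of these bears on differences between periods or between units. It is permissive. There is no schedule, no selection rule and no minimum time off for a unit. Statistical analyses describes paired t-tests on assessment scores and gives no analysis of falls counts. Pre-study quarters, unit baseline rates and patient-day denominators appear nowhere.

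**The concern.** In a non-randomised unit-by-quarter comparison, the intervention effect has to be separated from two other things: each unit's usual fall rate, and change over calendar time. The units range from general wards to IMCU and Hospice, so equal underlying rates cannot be presumed. A unit that is always on gives no information about its own rate when off, and a unit that is always off gives none about its rate when on. If designation does not change, which the text permits, the on/off contrast is simply a contrast between different units.

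Quarters before first enrolment would supply an off period for every unit. Since the plan describes quarterly unit reporting as routine, such quarters may well be available, yet the plan does not call on them. At stake is whether the falls aim can be answered at all under some permitted schedules, and how precisely under others.

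**Working it through.** **Inputs from the documents.** There are seven units (Study Units). Enrolment is "expected to be enrolled at JHMC over the course of two years" (Sample Size) and does not start at a quarter boundary, so there are 7 full calendar quarters after the partial first one. Each unit then has at most three same-season pairs a year apart (quarters 1 and 5, 2 and 6, 3 and 7). The plan gives no falls rate, effect size or precision, so there is no falls figure to reproduce.

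**Assumptions.** Expected falls are μ per unit-quarter, equal across units, with μ = 6 (range 3 to 12). There is no overdispersion. The pre-study window is 8 quarters, all off. The model has unit effects and a separate effect for each quarter.

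**Formula.** The information on the log rate ratio is μ × SS, where SS is the residual sum of squares of the on-indicator after unit and quarter effects. For a complete 7 × T grid:

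SS = N − ΣR²/T − ΣC²/7 + N²/(7T), and SE = 1/√(μ × SS).

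N is the number of on unit-quarters, R the on quarters per unit, C the on units per quarter, and T is 7 without or 15 with the earlier quarters. Ratios of SE between T = 7 and T = 15 do not depend on μ.

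| Schedule | N | ΣR² | ΣC² | SS, T = 7 | SS, T = 15 | Change |
|---|---|---|---|---|---|---|
| 4 of 7 units on throughout | 28 | 196 | 112 | 0 | 6.40 | not estimable → estimable |
| One unit added per quarter | 28 | 140 | 140 | 4.00 | 6.13 | variance −35%, SE −19% |
| 4 on, one pair swapped after quarter 3 | 28 | 172 | 112 | 3.43 | 8.00 | variance −57%, SE −35% |
| 4 and 3 units alternating every quarter | 25 | 91 | 91 | 11.76 | 11.89 | variance −1% |
| Full exchange of 4 and 3 units after quarter 3 | 24 | 84 | 84 | 11.76 | 11.89 | variance −1% |
| All 7 on throughout | 49 | 343 | 343 | 0 | 0 | not estimable either way |

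Staggered row worked through: 28 − 140/7 − 140/7 + 784/49 = 4.00, and 28 − 140/15 − 140/7 + 784/105 = 6.13. The variance ratio is 4.00/6.13 = 0.65 and the SE ratio √0.65 = 0.81.

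With a random half of the units on (300 draws), mean SS goes from 8.97 to 9.78, an SE ratio of √(8.97/9.78) = 0.96. With season plus linear trend in place of quarter effects it goes from 9.49 to 12.32, an SE ratio of 0.88.

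For all units on, replacing the quarter effects by season plus linear trend gives SS 0 without and 5.49 with the earlier quarters.

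**In absolute terms at μ = 6.** Power is Φ(|ln 0.7|/SE − 1.96), for an assumed 30% reduction in the unit's rate at two-sided 0.05.
- Fixed designation: not estimable → SE 0.161, power 60%.
- Staggered: SE 0.204 → 0.165, power 42% → 58%.
- One pair swapped: SE 0.220 → 0.144, power 37% → 70%. Over μ = 3 to 12 the SE runs from 0.312 to 0.156 without the earlier quarters, and from 0.204 to 0.102 with them.
- Alternating: SE 0.119 → 0.118, power about 85% both ways.

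**The case against.** The strongest reply is that the worst cases need schedules that defeat the plan's stated purpose. Designation is changed precisely to allow comparison, and when it changes substantially the pre-study quarters add almost nothing. This stands. A reader might infer that the falls effect cannot be estimated under this plan; the documents do not support that, because they permit schedules under which it is estimated from within-study data alone. Equally, they do not commit to any such schedule.

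A reader might also infer that the hospital demonstrably holds the earlier counts. The text says only that it collects and reports quarterly unit falls. It does not say how far back, whether all seven units existed unchanged, or whether patient-days are available. Earlier quarters are a reasonable inference that the sponsor must confirm.

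The earlier quarters may also not be clean. Background and significance describes a 2016 avatar study on three medical-surgical units at this hospital, and prior exploratory work on preventing falls in hospital. The date of first enrolment is not given, so an open-ended window could reach into avatar-exposed periods.

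Two further points stand. The plan speaks of annual changes, so season is an interpretation. And the opening summary refers to patient medical records for the incidence of falls, which sits uneasily with Study Units. If falls can be attributed to individual patients, the randomised arms could be compared directly, and this should be settled first.

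**Conclusion.** The point holds, with a size that depends on the schedule. With fixed designation of some units, the effect is inseparable from those units' own fall rates unless earlier quarters are used. With staggered or sparse switching it is estimable but imprecise, and eight earlier quarters reduce the SE by 19% to 35% in the schedules tried. With a random half of the units on the gain is about 4% in SE, and with alternation or full exchange about 1% in variance.

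It would be too strong to say that earlier quarters rescue every schedule. With all units on throughout and separate quarter effects, they do not; the effect is then identified only by assuming a season-plus-trend form for calendar time.

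The relative gains rest on equal expected counts across units and comparability of the earlier quarters. The SEs and power also rest on the assumed μ, the assumed 30% reduction and no overdispersion. Overdispersion would widen every SE.

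**What to change.** 1. Fix the quarterly designation schedule in advance, with real on and off periods for each unit. This alone removes most of the problem.
2. Confirm that quarterly falls reports and patient-days exist for each of the seven units before first enrolment. If so, extract a window of fixed length (for example 8 complete quarters), chosen before the data are seen and used in full. Exclude or flag quarters that overlap the 2016 avatar study or other earlier avatar use.
3. Prespecify one Poisson or negative binomial model for all unit-quarters, with a patient-day offset, allowance for overdispersion, unit effects and separate quarter effects. This compares each unit's change with the change in the other units.
4. If all units are on throughout, replace the quarter effects by season plus linear trend, and state that the result relies on that assumption.
5. Reconcile the opening summary with Study Units on where falls data come from.

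The cost is one retrospective pull of reports and some analysis wording, with no extra patients or procedures. The downside is reliance on the comparability of earlier quarters. The earlier quarters do not cure dilution by usual-care and non-enrolled patients in the same unit counts, carry-over of patients still enrolled after a unit is switched off, or non-random choice of units.

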Delirium occurrence rates for hospitalized older adults range from 29-64%. Although 30-50% of delirium is preventable, it frequently goes unrecognized until acute and potentially devastating. The Hospital Elder Life Program (HELP) is a multidimensional clinical strategy that is effective in preventing delirium, but labor intensive. This randomized controlled study will test an innovative method to implement the HELP approach: a tablet-based digital avatar that can see, hear, and talk with a patient using speech-to-text technology. The avatar platform has already been validated at Jamaica Hospital in a previous study in 2016: “GeriJoy: The Use of an Avatar Virtual Service Animal to Improve Outcomes in Hospitalized Older Adults” as well as in multiple published studies to effectively provide psychosocial support to older adults across varied clinical settings. This study will focus on discerning the relative impact of implementing HELP through this technology. Participants aged 65+ will be randomly assigned to receive one of the following interventions in addition to usual care throughout their hospitalization: 1) an avatar delivering HELP protocols and socialization; or 2) no intervention beyond usual care. Participants will be assessed by the investigators upon admission to the study and reassessed upon 24-hour discharge notification using the Short Portable Mental Status Questionnaire (SPMSQ), Memorial Delirium Assessment Scale, and Short CAM (Confusion Assessment Method). Based on patient medical records of sedation, restraints and incidence of falls and delirium, pre- and post-assessment scores will be compared using paired t-tests to determine outcomes among the groups. If the avatar is effective in improving outcomes by providing HELP interventions, the number of patients who benefit from HELP could increase greatly due to technology-enabled cost efficiencies, and protocol and data collection standardization across many sites.

Specific aims/hypotheses

For hospitalized older adults, will the use of an avatar delivering HELP protocols...

1. decrease delirium incidence and severity,
2. decrease falls and falls with injury,

..more than usual care?

Background and significance

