Sample inclusion and exclusion criteria: All patients over age 65 on the pilot units who can provide informed consent or who have a proxy who can provide informed consent will be assessed by the investigators. Those who consent will be randomly assigned to one of the two treatment conditions unless they meet any of the exclusion criteria: a.) aggression or combativeness with intent to harm self or others, b.) alcohol or drug withdrawal, c.) severe hearing impairment and simultaneous severe vision impairment, despite assistive devices, d.) cannot verbalize fluently in either Spanish or English, e). on 1:1;if a study subject is put on 1:1 during the duration of the study, he/she will be unenrolled from the study, f) expected to be discharged within the next 24 hours.

Instruments

Pre- and post-intervention:

1. Short Portable Mental Status Questionnaire
2. Short CAM (Confusion Assessment Method) – also conducted during each daily round
3. Memorial Delirium Assessment Scale – if CAM screens positive

Statistical analyses: Demographic variables including age, gender, education, race/ethnicity, and living arrangements will be collected to determine equivalency of study groups. Pre-and post-assessment scores will be compared using paired t-tests to compare means at baseline and at hospital discharge within each group, and between groups. All data will be analyzed using the Statistical Package for Social Sciences software (SPSS, Inc. Chicago, IL). Statistical significance will be defined as $p \leq 0.05$.

Additional Information

Photos of Avatar

Figure D.8.1: A hospitalized older adult in South Carolina enjoys the company of an avatar as it plays music and shows a photo. A “fisheye lens” mounted to the top of the avatar device enables wide-angle visual monitoring, to enable appropriate reaction by the avatar to not only the patient’s facial and body language cues, but also any dangerous unassisted transfers, tugging on IV lines, etc. To help with re-orientation, the window behind the avatar reflects the actual weather report, and the lighting of the avatar’s environment reflects day or night status. A video showing the patient talking to the avatar and singing along is available at <https://www.youtube.com/watch?v=WfWjazOmKUk>

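### Patients who already have delirium are eligible, but the plan defines neither an at-risk population nor incident delirium, and its only stated analysis does not estimate the incidence named in aim 1

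*Combined protocol and SAP*

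**What the plan says.** All references are to the combined protocol and SAP.

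- **Specific aims/hypotheses.** The first aim is to "decrease delirium incidence and severity" by more than usual care does.
- **Sample inclusion and exclusion criteria.** The eligible group is "All patients over age 65 on the pilot units who can provide informed consent or who have a proxy who can provide informed consent". Exclusions a to f cover aggression, withdrawal, combined severe sensory loss, language, being on 1:1, and imminent discharge. None is delirium or a positive CAM. A participant placed on 1:1 later is unenrolled.
- **Opening summary.** "Participants will be assessed by the investigators upon admission to the study and reassessed upon 24-hour discharge notification". The same paragraph introduces the comparison of scores with the words "Based on patient medical records of sedation, restraints and incidence of falls and delirium", which makes the medical record a source for delirium incidence.
- **Instruments.** The list includes "Short CAM (Confusion Assessment Method) – also conducted during each daily round" and "Memorial Delirium Assessment Scale – if CAM screens positive".
- **Statistical analyses.** The method is "paired t-tests to compare means at baseline and at hospital discharge within each group, and between groups". The variables listed for checking that the groups are equivalent are demographic only.

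No section says which patients are at risk of new delirium, what counts as an incident case, or whether entry CAM status enters the analysis by restriction, stratification or adjustment.

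**The concern.** A patient who is delirious at entry cannot develop delirium as a new event during that same episode. Incidence therefore needs a denominator of patients free of delirium at entry and a rule for onset after randomisation. The plan has neither, although it admits patients who may already be delirious, including some who need a proxy to consent.

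Two things are at stake. First, the incidence half of aim 1 has no analysis that answers it. Second, with no rule fixed in advance, the analyst may choose after seeing the data between all patients and entry-negative patients, and between chart delirium and CAM delirium. These choices can give materially different ratios. The Study design section says that randomisation matters mainly for the delirium data, so this is the trial's main randomised comparison.

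**Working it through.** **1. Does the stated analysis estimate incidence?**

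Code the Short CAM as 0 or 1 at entry and at discharge. Over all participants, the mean paired change is

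P(negative at entry, positive at discharge) − P(positive at entry, negative at discharge).

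This nets onset against resolution, and it can be zero when many new cases occur. It also ignores the daily rounds: an episode that starts after entry and clears before discharge scores as no change. Under the Instruments wording, MDAS is scored only when the CAM is positive. A paired MDAS change then exists only for patients positive at both times, which leaves out every incident case. None of these quantities is incidence.

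**2. What happens if delirium is tallied over everyone?**

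The plan gives no figure to reproduce here. Its 3,650 is expected enrolment, with no delirium rate, effect size or power attached.

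Inputs:
- n = 1,825 per arm, which is 3,650 / 2. The 1:1 ratio is assumed; the plan states none.
- i = 0.20, new delirium in at-risk controls (assumed).
- r = 0.70, the true risk ratio, from the lower end of the summary's 30-50% preventable share, read as a relative reduction.
- p = 0.10, 0.20 or 0.30, delirium at entry (assumed).
- The avatar has no effect on whether delirium is already present (assumed).

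Formulas: control = p + (1−p)i; avatar = p + (1−p)ir; z = difference / √(sum over arms of π(1−π)/n), where π is the arm's proportion. The at-risk comparison is 0.20 against 0.14 with n = 1,825(1−p).

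| p | Control | Avatar | All-patient ratio | z, all patients | z, CAM-negative only |
|---|---|---|---|---|---|
| 0.10 | 0.280 | 0.226 | 0.807 | 3.76 | 4.59 |
| 0.20 | 0.360 | 0.312 | 0.867 | 3.07 | 4.33 |
| 0.30 | 0.440 | 0.398 | 0.905 | 2.57 | 4.05 |

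For p = 0.20: 0.20 + 0.80 × 0.20 = 0.360; 0.20 + 0.80 × 0.14 = 0.312; 0.312 / 0.360 = 0.867.

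**3. How much power is lost?**

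The summary gives delirium occurrence of 29-64%, without a split into existing and new cases. Fix control occurrence at one of those values, take a 30% reduction in new cases, and use a two-sided 0.05 test (sidedness is not stated). Power = Φ[(|d| − 1.96·SE0)/SE1], where d is the difference in proportions and SE0 and SE1 are the pooled and unpooled standard errors.

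- **29% occurrence, 20% at entry.** New delirium in controls is (0.29 − 0.20)/0.80 = 0.1125, against 0.1125 × 0.70 = 0.07875 with the avatar. Over everyone this is 0.290 against 0.263, so the true 30% reduction appears as 9.3%. Power is 44.6% in all 1,825 per arm and 87.3% in the 1,460 CAM-negative per arm.
- **29% occurrence, 10% at entry.** The reduction appears as 19.7%. Power is 97.5% in all patients and 99.7% in CAM-negative patients.
- **64% occurrence, 10%, 20% or 30% at entry.** The reduction appears as 25.3%, 20.6% or 15.9%. Power over everyone stays above 99.9%.

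**The case against.** A reader might infer that the trial cannot measure incidence. The documents do not support that. The Short CAM is taken at entry, at each daily round and before discharge, so the data show who was negative at entry and who turned positive later. What is missing is the analysis definition.

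A reader might also infer that the plan counts an entry-positive patient as a case in both arms. No section says so. Incidence ordinarily means new cases, and the all-patient risk ratio modelled above appears nowhere in the plan. The dilution is therefore what would follow from one reading that the text leaves open. That leaves the definition gap in place.

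Nor is enrolling delirious patients a fault in itself. Aim 1 includes severity, and these patients inform that half.

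The size of the effect is open to challenge. Entry prevalence, incidence and allocation ratio are all assumed. Exclusions for aggression and for being on 1:1 may remove some delirious patients, and it is plausible but nowhere stated that proxy-consented patients are more often delirious. In the table, every all-patient z exceeds 1.96; taking Φ(z − 1.96), power is about 96%, 87% and 73%. This limits the argument about power. It does not touch the bias towards 1 under an all-patient tally, which a larger sample cannot cure.

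**Conclusion.** The point holds as a gap in the analysis plan. Followed as written, the plan does not answer the incidence half of aim 1: it has no at-risk population and no incident-case definition, and its paired t-tests estimate something else. This conclusion rests on the text alone.

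The numerical size is conditional. Under an all-patient tally and the stated assumptions, a true ratio of 0.70 would be reported as roughly 0.81 to 0.90. Power loss is serious only where occurrence is low and entry prevalence high, as in the case of about 45% against 87%. At high occurrence it is negligible, but the estimate is still diluted.

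**What to change.** Amend the Instruments and Statistical analyses sections as follows.

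1. State that the entry Short CAM is completed before randomisation. The current wording does not fix that order. A subset defined by a pre-randomisation result keeps the randomised comparison.
2. Define the incidence population as randomised patients who are CAM-negative at entry.
3. Define incident delirium as the first positive Short CAM, at a daily round or at discharge, after randomisation.
4. For this endpoint, replace the paired t-test with a between-arm comparison of proportions or of time to onset.
5. For patients unenrolled because they are put on 1:1, keep the outcome data up to unenrollment in the analysis. Otherwise new cases may drop out after randomisation.
6. Report entry-CAM-positive patients separately for severity and resolution.

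The cost is protocol wording, plus attention to the order of the entry assessment and randomisation. No new data and no change in eligibility are needed. The small downside is a smaller denominator for the incidence comparison, which in the cases worked above still gives the more sensitive test.

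### The two accounts of when the Memorial Delirium Assessment Scale is given differ; under the CAM-triggered one the paired severity comparison omits new delirium cases and may select on discharge CAM status

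*Combined protocol and SAP*

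**What the plan says.** The opening summary of the combined protocol and SAP states: "Participants will be assessed by the investigators upon admission to the study". They are then to be "reassessed upon 24-hour discharge notification using the Short Portable Mental Status Questionnaire (SPMSQ), Memorial Delirium Assessment Scale, and Short CAM". No condition is attached to the Memorial Delirium Assessment Scale (MDAS).

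The Instruments section, in its pre- and post-intervention list, gives item 3 as "Memorial Delirium Assessment Scale – if CAM screens positive". Item 2, the Short CAM, is "also conducted during each daily round".

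Specific aims/hypotheses, Aim 1, is to "decrease delirium incidence and severity". Statistical analyses plans paired t-tests to "compare means at baseline and at hospital discharge within each group, and between groups". No section assigns a score or rank to CAM-negative patients, gives a missing-data rule, or defines a separate analysis set for severity.

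**The concern.** A paired test needs two scores from the same patient. If MDAS is given only after a positive CAM, some patients have one score or none and drop out of the severity comparison. Whoever is CAM-negative at entry has no baseline score, so patients who become delirious in hospital are left out. Those are the cases a prevention trial targets.

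If the trigger works at each assessment, patients whose delirium resolves also drop out, because they have no discharge score. Membership of the analysed set then depends on CAM status at discharge, which the avatar is meant to change. The retained patients in the two arms are no longer comparable by randomisation, and the severity half of Aim 1 loses the protection that randomisation was meant to give it.

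**Working it through.** **1. What each reading of the trigger retains** (entry/discharge CAM status)

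| Pattern | MDAS for everyone (summary) | Trigger per assessment | Trigger per patient, CAM-positive at entry |
|---|---|---|---|
| +/+ | pair | pair | pair |
| +/- (resolved) | pair | no discharge score | pair |
| -/+ (new) | pair | no baseline score | no pair |
| -/- | pair | no scores | no scores |

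New cases are lost under both CAM-triggered readings. Letting any positive daily CAM trigger a discharge MDAS would not recover them, since the baseline score would still be absent. Selection on a post-randomisation outcome arises under the per-assessment reading but not under the per-patient reading.

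**2. The plan's own figure.** Sample Size says "A total of 3,650 patients (avatar and usual care) are expected to be enrolled" over two years with a 4-day average stay. One slot gives 730/4 = 182.5 patients, so 3,650 corresponds to 3,650/182.5 = 20 concurrent slots. That number is not stated. The total is a throughput figure with no power, effect size or SD attached.

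**3. Assumed inputs.** 1,825 per arm (3,650 split 1:1); MDAS SD 5; entry and discharge scores bivariate normal with correlation r = 0.3, 0.6 or 0.8; one CAM threshold; a uniform avatar benefit of 1 point (0.2 SD); two-sided 0.05, tested by a Welch t-test on change. No unenrolment is modelled. Two further points are inferred: MDAS is the severity measure, because no other severity score is listed, and the between-group test compares paired change.

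**4. Per-assessment reading, 20% CAM-positive at entry and 9% at discharge.** The threshold is 0.842 SD. The discharge mean is -0.5 SD in usual care (9.0% positive) and -0.7 SD with the avatar (6.2% positive).

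- Pairs = 1,825 × P(positive at both times): 62, 100, 133 in usual care and 45, 74, 97 with the avatar, for r = 0.3, 0.6, 0.8.
- Total with a pair: 107 to 231 of 3,650, i.e. 2.9% to 6.3%.
- New cases left out: 102, 64, 31 in usual care; 68, 38, 15 with the avatar.
- Resolved cases left out (365 positive at entry minus pairs): 303, 265, 232 in usual care; 320, 291, 268 with the avatar.

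**5. Range over CAM positivity, same reading.** Share of the shift seen and power are from simulation.

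| Entry / discharge CAM-positive | Patients with a pair | Share of the 1-point shift seen | Power |
|---|---|---|---|
| 20% / 9% | 3-6% | 25-63% | 6-44% |
| 29% / 20% | 8-14% | 34-67% | 13-82% |
| 64% / 50% | 34-42% | 48-76% | 49% to about 100% |

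The 29% and 64% echo the occurrence range in the opening summary. That range describes delirium occurrence, not CAM positivity at study entry, so it does not settle which row applies.

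**6. Per-patient reading, 20% at entry.** Pairs = 0.20 × 1,825 = 365 per arm, and the full 1-point difference is seen. The variance of change among entry-positives, in SD units, is (1 - r)² × 0.219 + (1 - r²), where 0.219 is the variance of a standard normal above 0.842. For r = 0.3 this is 1.017. The standard error is √(1.017 × 2/365) = 0.0746, so z = 0.2/0.0746 = 2.68 and power is about 76%. For r = 0.6 and 0.8 power is about 91% and 99%.

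**7. Limiting cases at 20%/9%, per-assessment reading.** With no effect, the paired test rejects in 5.0-5.4% of simulated trials. If the avatar lowers MDAS by 1 point in CAM-positive patients and changes nobody's CAM status, the paired difference is 1.00 (unbiased), with power 38%, 61% and 89%.

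**The case against.** The strongest reply is that the plan can be read more kindly. Item 3 stands under a pre- and post-intervention list, so a patient CAM-positive at entry might get MDAS at both times. The subset is then fixed at baseline, resolved cases stay in, and step 6 shows no dilution. This stands: selection on discharge status is conditional on the reading. What remains on that reading is that new cases still have no pair, and the text does not say which reading is meant.

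The summary may also be only an abbreviation of the Instruments list. That is plausible, but staff and analysts still need one rule.

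A reader might infer that only 3-6% of patients will have a severity pair and that the analysis is bound to be underpowered. The documents do not support that. They give no CAM positivity at entry or discharge, and step 5 shows how far the answer moves.

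A reader might also infer that the comparison could turn a benefit into apparent harm or produce false positives. Under a uniform benefit the paired comparison is diluted, not reversed, and with no effect it holds its level. Reversal can be constructed for an unpaired mean among CAM-positive patients, but the plan does not name that analysis.

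**Conclusion.** The point holds in a conditional form. The two statements on MDAS differ and must be reconciled. Under the Instruments wording, the planned paired severity comparison omits new cases on either reading of the trigger. If the trigger is per assessment, it also omits resolved cases and rests on a subset selected after randomisation, in which a uniform 1-point benefit shows as roughly a quarter to three quarters of its true size across the assumptions tried. If the trigger is per patient, there is no such selection.

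The omission of new cases follows from the text, once MDAS is taken as the severity measure and the comparison as one of paired change. Every magnitude is assumed. If the avatar changes severity without changing CAM status, the paired difference is unbiased. CAM-based incidence is untouched, so the point does not undermine the delirium aim as a whole. Confidence is medium, and the change should be made because it concerns a stated part of Aim 1.

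**What to change.** Reconcile the opening summary with Instruments item 3, and state whether the trigger is per assessment or per patient. Then make the between-arm severity comparison at the discharge assessment over all randomised patients, in whichever form matches the intended schedule:

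- **If the CAM trigger stays:** place CAM-negative patients at the lowest rank and use a rank or proportional-odds method adjusted for baseline CAM status. Do not carry a baseline MDAS forward. Label the result a combined incidence-severity measure. In the 20%/9% scenario its power is about 90%, against 89-90% for a plain test of discharge CAM status, so nearly all of it comes from incidence. The cost is analysis wording, and severity is not isolated.
- **If MDAS for everyone is intended:** compare discharge MDAS between arms, adjusted for baseline MDAS. This needs up to 3,650 × 2 = 7,300 administrations, against about 3,650 × (0.20 + 0.09) = 1,058 under the trigger at the assumed rates: about 6,200 more, at visits already planned. At 64%/50% the excess falls to 7,300 - 3,650 × 1.14 = 3,139. Power exceeds 99% for the uniform 1-point shift at 20%/9%, but is only 9-15% if the benefit is confined to CAM-positive patients with CAM status unchanged.

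Under either form, patients without a discharge assessment must not receive the best rank or score by default; vary their value in a sensitivity analysis. This may include those covered by the rule "if a study subject is put on 1:1 during the duration of the study, he/she will be unenrolled from the study". Report MDAS among CAM-positive patients, including the paired analysis, as descriptive.
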